4.2.2.1.7 Supplementary Analyses of the 1st Key Secondary Endpoint

Additionally, PAINS-pNF chronic target PN pain intensity actual scores as well as the change from baseline at each cycle will be summarised descriptively by visit and study intervention arm for FAS and Pain FAS. If there are instances of early crossover, then some cycles prior to Cycle 12 will summarise data of placebo subjects who have already crossed over to selumetinib.

Summary statistics will include n, mean, standard deviation, min, Q1, median, Q3, and max, where n is the number of subjects contributing to the summary statistics for the visit.

This descriptive analysis in the Pain FAS will be repeated only for the randomised period by considering the three missing cycle score rules mentioned in Section [4.2.2.1.6](#).

Summary statistics will also be presented by attributable versus non-attributable reasons (see Section [3.3.9](#)) only for the randomised period.

Plots of the mean scores, as well as the changes from baseline and the associated 95% CIs by cycle will be produced for the randomised period.

The empirical cumulative distribution function (eCDF) of change from baseline by study intervention arm will be plotted at Cycle 12 for the Pain FAS. The eCDF will be the cumulative percent frequency (Cum_Pct) of the change from baseline in the PAINS-pNF chronic target PN pain intensity actual score by study intervention arm saved by default in the output dataset of the SAS procedure proc freq.

4.2.2.2 Plexiform Neurofibroma Quality of Life Scale

4.2.2.2.1 Definition

The PlexiQoL is a patient-derived quality of life (QoL) measure specific to adults with NF1-associated PNs. It assesses the impact of PNs on patients' ability to fulfil their human needs. The scale adopts the needs-based model of QoL and joins a large portfolio of high-quality outcome measures that are widely used in international clinical studies (see for example [Marzo-Ortega et al 2005](#); [McKenna et al 2006](#); [Tay et al 2011](#)). The scientifically rigorous methodology employed in the development of the PlexiQoL ensures accurate and valid measurement of the impact of the condition and the value of potential treatments to the lives of patients.

The PlexiQoL questionnaire is planned to be collected at baseline and Cycles 2, 4, 8, and 12 during the randomised period as well as at Cycles 16, 20, 24, 30, and every 6 weeks onwards as per the Schedule of Activities (see Section 1.3 of the CSP).

The randomised period is defined in Section [3.3.2.2](#).

4.2.2.2.2 Derivations

The measure consists of 18 dichotomous items with 0 = "Not True" and 1 = "True". Scores are summed to a maximum of 18, with lower scores indicating better quality of life. According to the PlexiQoL user manual, it is recommended that for respondents with between one and three missing responses (that is, cases with no more than 20% missing data), the total score is calculated as follows: $T=18*x / (18-m)$, where T is the final total score, x is the item summation score, and m is the number of missing items. Cases with more than three missing responses cannot be allocated a total score.

The change from baseline to the end of each cycle in PlexiQoL total score will be derived as the PlexiQoL total score at the specific cycle minus baseline PlexiQoL total score.

4.2.2.2.3 Intercurrent Events

The intercurrent event strategy for the 2nd key secondary estimand is described in [Table 10](#).

Table 10: Intercurrent Event Strategy for the 2nd Key Secondary Estimand

Intercurrent event	Strategy	Details
Randomised study intervention discontinuation	Hypothetical strategy	PlexiQoL total scores following randomised study intervention discontinuation will not be collected and will be modelled through direct likelihood techniques.

Early crossover from placebo to selumetinib in patients with documented progression on imaging (as determined by ICR per REiNS criteria)	While on-treatment strategy	PlexiQoL total scores after early crossover from placebo to selumetinib will be set to missing.
Prolonged study intervention interruption (defined as a study intervention interruption greater than or equal to 28 continuous days of no study intervention)	While on-treatment strategy	The following rules will be followed to align with the while on-treatment strategy: 
 - PlexiQoL total scores during the first 28 days of prolonged treatment interruption will be included. - PlexiQoL total scores after the first 28 days of prolonged treatment interruption will be excluded. - PlexiQoL total scores from the day of study intervention recommencement will be included.
Target PN resection	Treatment policy strategy	PlexiQoL total scores after a target PN surgical resection will be included in the analysis.

ICR, independent central review; PlexiQoL, Plexiform Neurofibroma Quality of Life scale; PN, plexiform neurofibroma; REiNS, Response Evaluation in Neurofibromatosis and Schwannomatosis.

4.2.2.4 Handling of Dropouts and Missing Data

Missing items within an assessment will be handled as in the previous section.

4.2.2.5 Primary Analysis of the 2nd Key Secondary Endpoint

The difference in the mean change from baseline in PlexiQoL total score at Cycle 12 between treatment groups (selumetinib minus placebo), standard error, 95% CI, and p-value will be assessed by LS means of an MMRM with randomised study intervention, cycle number, geographical region and average baseline chronic target PN pain intensity group as categorical fixed effects; the baseline PlexiQoL total score as a continuous covariate; and treatment-by-cycle number and baseline PlexiQoL total score-by-cycle number interactions. Parameters will be estimated with the REML approach, and the Kenward-Roger approximation is used to estimate the degrees of freedom.

The analysis will be performed on a subset of the FAS population with an evaluable baseline assessment and at least one evaluable post-baseline assessment. Evaluable assessment is defined as a PlexiQOL total score. Data collected during the randomised period (see Section 3.3.2.2) will be included, adhering to the intercurrent event strategy (refer to Section 4.2.2.2.3).

The analysis will be conducted using PROC MIXED in SAS using the same model specifications as specified for the 1st key secondary endpoint (see Section 4.2.2.1.5). All main effects and the interaction terms will remain in the model, regardless of significance.

In addition to the Cycle 12 estimate, the model will present LS mean estimates for each treatment group and their differences, standard errors, 95% CIs, and p-values (where applicable and with statistical significance effects being interpreted as nominally significant) for mean changes from baseline to each cycle during the randomised period (based on the treatment-by-cycle interaction coefficient) and the average over the randomised period (based on the treatment coefficient). A plot of the LS means accompanied by the 95% CI will be produced.

4.2.2.2.6 Sensitivity Analyses of the 2nd Key Secondary Endpoint

Analyses to assess the robustness to assumptions of missing data.

The analyses use MI and apply the planned primary analysis to the imputed outcomes, combining the statistics using Rubin's rules. These two supplementary analyses only vary as to the scenarios implemented for the intercurrent event of treatment discontinuation, as follows:

- Multiply impute reversion to baseline after discontinuation of treatment (Ratitch et al 2013) up to Cycle 12: this analysis provides an estimate for the estimand that targets the hypothetical approach, using the assumption that subjects who discontinue treatment gain no improvement in change of baseline. For the template code to implement the reversion to baseline, see the supplementary appendix to Ratitch et al 2013, under the code heading “Pattern imputation based on reasons for discontinuation”.
- MI using attributable and non-attributable dropout reasons: hypothetical strategy with MNAR with reversion to baseline for scores after study intervention discontinuation due to attributable dropout reasons and MAR after study intervention discontinuation due to non-attributable dropout reasons. The reason for study intervention discontinuation will be categorised as attributable or non-attributable as outlined in Section 3.3.9.

Refer to Section 4.2.2.1.6.1 for details on identifying cycles eligible for imputation using reversion-to-baseline and for a summary of the approach.

4.2.2.2.7 Supplementary Analyses of the 2nd Key Secondary Endpoint

PlexiQoL total score, as well as the change from baseline at each cycle will be summarised descriptively by study intervention arm. If there are instances of early crossover, then some cycles prior to Cycle 12 will summarise data of placebo subjects who have already crossed over to selumetinib. Summary statistics will include n, mean, standard deviation, min, Q1, median, Q3 and max.

Graphical plots of the mean scores, as well as the change from baseline and associated 95% CIs by cycle will be produced for the randomised period.

Summary statistics will also be presented by attributable versus non-attributable reasons (see Section [3.3.9](#)) only for the randomised period.

The analysis will be performed on the FAS and the Pain FAS.

4.2.3 ORR (Single-Arm)

4.2.3.1 ORR (Single-Arm) Definition

ORR will be defined as the proportion of patients who have a cCR (defined as the disappearance of the target PN, confirmed by a consecutive scan within 3 to 6 months after the first response; see Section [4.2.1.2](#)) or cPR (defined as a target PN volume decrease $\geq 20\%$ compared to baseline, confirmed by a consecutive scan within 3 to 6 months after the first response; see Section [4.2.1.2](#)) as determined by ICR per REiNS criteria.

The ORR will be derived using while on-treatment MRI volumetric assessments (see Section [3.3.2.1](#)).

Any cCR or cPR which occurred after a subsequent NF1-PN treatment (following study intervention discontinuation) will not be included in the numerator for the ORR calculation (where the selumetinib FAS will be the denominator). Patients with no post-baseline MRI assessments will be considered as non-responders (not having a cCR or cPR).

The confirmation by a consecutive scan within 3 to 6 months will be derived as CR/PR achieved on consecutive visits with no missed visits as per assessment schedule. If MRI assessments are excluded due to prolonged study intervention interruption (as described in Section [4.2.1.6](#)), then the visit will be considered a missed visit.

If the interim analysis takes place, at DCO2 the same partial volume strategy defined in [4.2.1.1](#) will be used for this endpoint and the ORR will be analysed using the scaled partial

volumes after DCO1 (third set of parameters), and a supplementary analysis will be performed using the non-adjusted partial volume after DCO1 (first set of parameters).

At the final DCO, the same partial volume strategy defined in [4.2.1.1](#) will be used for this endpoint. At the final DCO, the ORR will be analysed using the scaled partial volumes after DCO2 (third set of parameters), and a supplementary analysis will be performed using the unadjusted partial volume after DCO2 (first set of parameters).

4.2.3.2 Best Objective Response Definition

The best objective response (BOR) will be calculated based on the overall visit responses from each on-treatment MRI assessment, as described in [Section 0](#). It is the best response a patient has had following the start of intervention, but prior to starting any subsequent NF1-PN therapy and up to and including progression or the last evaluable MRI assessment in the absence of progression. The categorisation of BOR will be based on REiNS using the following response categories: cCR, CR, cPR, PR, SD, PD, and NE.

The different ways of achieving a BOR of cCR, CR, cPR, or PR are shown in [Table 11](#).

Table 11: Scenarios for Best Objective Response

Post-baseline Visit N	Post-baseline Visit N+1	BOR
PR	PR/CR	Confirmed PR (cPR)
PR	SD/PD/NE	Unconfirmed PR
CR	CR	Confirmed CR (cCR)
CR	PR/SD/PD/NE	Unconfirmed CR
SD/NE	CR	Unconfirmed CR
SD/NE	PR	Unconfirmed PR
NE	NE	NE

BOR, best objective response; CR, complete response; NE, not evaluable; PD, progressive disease; PR, partial response; SD, stable disease.

BOR will be determined programmatically based on REiNS from the overall visit response using all data up until the first progression event or the last evaluable MRI assessment in the absence of progression. BOR will be derived using the on-treatment MRI volumetric assessments (see [Section 3.3.2.1](#)). The denominators will be consistent with those used in the single-arm ORR analysis.

Patients with no post-baseline MRI assessments will be considered as non-responders. For patients whose progression event is death, the BOR will be calculated based on all evaluable MRI assessments prior to death using the while on-treatment MRI volumetric assessments (see [Section 3.3.2.1](#)).

At DCO2, the BOR will be analysed using the ICR data with the scaled partial volume after DCO1 (third set of parameters) as described in Section 4.2.1.1 .

At the final DCO, the BOR will be analysed using the ICR data with the scaled partial volume after DCO2 (third set of parameters) as described in Section 4.2.1.1.

4.2.3.3 Intercurrent Events

The approach for intercurrent events mostly follows the same as outlined for the primary endpoint in Section 4.2.1.7 However, the first intercurrent event for the primary endpoint, as detailed in Table 8, will change to be ‘Post randomised study intervention discontinuation due to any reason’ since early crossover from placebo is not relevant to the analysis of single-arm ORR, as analysis is performed on patients randomised to selumetinib (see Section 4.2.3.4). And any post randomised study intervention discontinuation should not be restricted to prior to Cycle 16, as the single-arm ORR is evaluated over the whole while on-treatment MRI volumetric assessments period (Section 3.3.2.1).

4.2.3.4 Primary Analysis of Single-Arm ORR

The primary analysis will include all patients randomised to selumetinib (selumetinib FAS), that is, a single arm assessment of ORR. Data obtained from the first selumetinib dose up until progression or the last evaluable assessment in the absence of progression, and while on-treatment MRI volumetric assessments (see Section 3.3.2.1) will be included in the assessment of single-arm ORR. Data are included as outlined in Section 4.2.3.1, adhering to the intercurrent event strategy (refer to Section 4.2.3.3).

The ORR will be presented with a corresponding 2-sided exact 95% CI based on the Clopper-Pearson method (Clopper and Pearson 1934).

Analyses will occur at DCO1, DCO2, and the final DCO. At DCO2 and the final DCO the partial volume strategy defined in Section 4.2.1.1 will be used for this endpoint. At DCO2, the ORR will be analysed using the scaled partial volumes after DCO1 (third set of parameters). At the final DCO, the ORR will be analysed using the scaled partial volumes after DCO2 (third set of parameters).

4.2.3.5 Supplementary Analyses of ORR

Supportive evidence of the primary endpoint of ORR will include the following:

- The ORR will be calculated based on all MRI volumetric assessments without excluding scans during study intervention interruption. MRI volumetric assessments data will be defined as data after the date of first dose of study intervention until the study intervention discontinuation date or DCO, whichever occurs first. The analysis will follow the same methods as for the primary analysis.

- A supplementary analysis will be performed including all randomised patients who received at least one dose of selumetinib (Extended Selumetinib FAS). In this analysis, the baseline MRI scan for patients randomised to placebo will be defined as the last MRI scan performed on placebo intervention prior to starting on selumetinib intervention. The ORR will be derived using while on-treatment MRI volumetric assessments (see Section 3.3.2.1).
- The BOR, defined as the BOR (see Section 4.2.3.2) recorded from the start of study intervention until prior to starting any subsequent NF1-PN therapy or up to and including progression or the last evaluable MRI assessment in the absence of progression, will also be summarised by category (cCR, CR, cPR, PR, SD, PD, or NE) in the selumetinib FAS and Extended Selumetinib FAS. BOR will be derived using the while on-treatment MRI volumetric assessments (see Section 3.3.2.1).

4.2.4 Duration of Response

4.2.4.1 Definition

For the subset of patients who have a cCR or cPR, DOR will be defined as the time from the date of the first documented response (which is subsequently confirmed) until the date of documented progression as assessed by ICR per REiNS criteria or death due to any cause. DOR will be derived using the while on-treatment MRI volumetric assessments (see Section 3.3.2.1). The end of response should coincide with the MRI assessment of progression or death from any cause used for the progression-free survival (PFS) endpoint (see Section 4.2.5). The date of the first documented response will be defined as the latest of the dates contributing towards the first response of PR or CR which is subsequently confirmed.

4.2.4.2 Derivations and Censoring Rules

If a patient does not progress following a response, then their DOR will use the PFS censoring (Section 4.2.5.2). The derivation formula for the DOR is date of PFS event or censoring – date of first response + 1. The DOR will be derived based on the actual MRI assessment dates and not visit dates.

4.2.4.3 Intercurrent Events

The approach for intercurrent events mostly follows the same as outlined for the primary endpoint in Section 4.2.1.7. However, the first intercurrent event for the primary endpoint, as detailed in Table 8, will change to be ‘Post randomised study intervention discontinuation due to any reason’ since early crossover from placebo is not relevant to the analysis of duration of response, as analysis is performed on patients randomised to selumetinib (see Section 4.2.4.4). And any post randomised study intervention discontinuation should not be restricted to prior to Cycle 16, as duration of response is evaluated over the whole while on-treatment MRI volumetric assessments period (Section 3.3.2.1).

4.2.4.4 Primary Analysis of DOR

Kaplan-Meier (KM) plots of DOR will be presented including a patients-at-risk table. Median DOR, 25th and 75th percentiles, and 95% CI will also be calculated together with the estimated percentage remaining in response and 95% CI using the KM method and presented in a summary table. The number and percentage of responding patients remaining in response at 8, 12, 16, 20, and 24 months post-response and every 6 months thereafter will also be summarised.

Only patients randomised to selumetinib (Selumetinib FAS) with a cCR or cPR prior to selumetinib discontinuation will be included in this analysis. Data are included as outlined in Sections 4.2.4.1 and 4.2.4.2, adhering to the intercurrent event strategy (refer to Section 4.2.4.3).

Swimmer plots that clearly show the profile of each patient who responds will also be produced. Additional graphical symbols to depict the start of the objective response, PD or death, and subsequent therapy will be added. “On treatment” will be designated with different colour from “post-treatment.”

4.2.4.5 Supplementary Analyses of DOR

- DOR will be calculated based on all MRI volumetric assessments without excluding scans during study intervention interruption. MRI volumetric assessments data will be defined as data after the date of first dose of study intervention until the study intervention discontinuation date or DCO, whichever occurs first. The analysis will follow the same methods as for the primary analysis of DOR.
- If there is at least one patient who progresses or dies after two or more consecutive missed MRI assessments, then the DOR analysis will be repeated without the specific PFS censoring rule (i.e., also including progression or death events after two or more consecutive missed MRI assessments). DOR will be derived using the while on-treatment MRI volumetric assessments (see Section 3.3.2.1).
- A supplementary analysis will be performed including all randomised patients who received at least one dose of selumetinib (Extended Selumetinib FAS) with a cCR or cPR prior to selumetinib discontinuation (e.g., the date of the first documented response is the date of the first documented response to selumetinib). In this analysis, the baseline MRI scan for patients randomised to placebo will be defined as the last MRI scan performed on placebo intervention prior to starting on selumetinib intervention. The DOR will be derived using the while on-treatment MRI volumetric assessments (see Section 3.3.2.1).
- Individual subject-level DOR (months) for each patient who responds will be summarised in a time-to-event listing for DCO2 and DCO3 for the Extended Selumetinib FAS.

4.2.5 Progression-Free Survival

4.2.5.1 Definition

PFS will be defined as the time from the date of randomisation until the date of progression by ICR per REiNS criteria or death due to any cause. PD is defined in Section 4.2.1.2. The appearance of new PN (with the exception of new discrete subcutaneous neurofibromas) or unequivocal progression of existing clinically relevant non-target PN is also considered PD as described in Section 4.2.1.3. PFS will be derived using the while on-treatment MRI volumetric assessments (see Section 3.3.2.1).

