### **9.4.2.3.3 Progression Free Survival**

Progression free survival will be derived using while on-treatment MRI volumetric assessments and is defined as the time from the date of first selumetinib dose until date of

progression by ICR per REiNS criteria or death (due to any cause), ie, date of event or censoring – date of the first dose of selumetinib + 1.

Participants who have not progressed or died at the time of analysis will be censored at the time of the latest date of assessment from their last evaluable REiNS assessment.

The analysis will include all participants randomised to selumetinib with measurable target PN at baseline per ICR who received at least one dose of selumetinib (Selumetinib FAS).

A supplementary analysis will be performed including all participants with measurable target PN at baseline per ICR who received at least one dose of selumetinib (Extended Selumetinib FAS). In this analysis, the baseline MRI scan for participants randomised to placebo will be defined as the last MRI scan performed on placebo treatment prior to crossing over to selumetinib treatment.

Full detail for the derivation of PFS while on-treatment and censoring rules will be documented in the SAP.

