Secondary	Progression-free survival (PFS) [single arm]	Selumetinib FAS, Extended Selumetinib FAS, and FAS (selumetinib arm only)	Treatment discontinuation: while on-treatment strategy; prolonged study intervention interruption (greater than 28 days): while on-treatment; strategy; target PN resection: treatment policy strategy; subsequent NF1-PN treatment: while on-treatment strategy	Percentage PFS at specified timepoints	4.2.5
To demonstrate the effectiveness of selumetinib by assessment of TTP in patients with NF1 who have symptomatic, inoperable PN.					
Secondary	Time to progression (TTP) [single arm]	Selumetinib FAS, Extended Selumetinib FAS, and FAS (selumetinib arm only)	Treatment discontinuation: while on-treatment strategy; prolonged study intervention interruption (greater than 28 days): while on-treatment strategy; target PN resection: treatment policy strategy; subsequent NF1-PN treatment: while on-treatment strategy	Percentage TTP at specified timepoints	4.2.6
To demonstrate the effectiveness of selumetinib by assessment of time to response (TTR) in patients with NF1 who have symptomatic, inoperable PN.					
Secondary	Time to response	Patients who have a confirmed response in	Not applicable for descriptive analysis	Percentage TTR at specified timepoints	4.2.7

	(TTR) [single arm]	Selumetinib FAS, Extended Selumetinib FAS, and FAS (selumetinib arm only)			
To demonstrate the effect of selumetinib relative to placebo by assessment of percentage change from baseline in target PN volume in patients with NF1 who have symptomatic, inoperable PN.					
Secondary	Best percentage change from baseline in target PN volume during the randomised period	Patients in the FAS with measurable target PN at baseline per ICR and at least one post-baseline target PN volume during the randomised period	Treatment discontinuation: while on-treatment strategy; prolonged study intervention interruption (greater than 28 days): while on-treatment strategy; target PN resection: treatment policy strategy; subsequent NF1-PN treatment: while on-treatment strategy	Mean difference between selumetinib and placebo in best percentage change from baseline in target PN volume using ANCOVA with covariates including baseline target PN volume, geographical region and average baseline chronic target PN pain group.	4.2.8

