4.2.5.2 Derivations and Censoring Rules

Patients who have not progressed or died at the time of analysis will be censored at their last evaluable MRI assessment. However, if the patient progresses or dies after two or more consecutive missed MRI assessments, the patient will be censored at the time of the latest evaluable MRI assessment prior to the missed visits. The details of censoring rules are listed in Table 12.

The derivation formula for PFS is date of PFS event or censoring – date of randomisation + 1.

If the patient has no evaluable MRI assessments post-baseline, they will be censored at Day 1 unless they die within two cycles from baseline. The PFS time will be derived based on actual MRI assessment dates and not visit dates.

Table 12: Summary of Censoring Guidelines for PFS

Assessment	Date of event, death or censoring	PFS outcome
Death, PD	MRI assessment of earliest sign of PD or death date if the event is death	Event
No PD or death at time of analysis or lost to follow-up	Latest evaluable MRI assessment	Censored
Death or PD after ≥ 2 missed assessments	Latest evaluable MRI assessment prior to the two missed assessments	Censored
No evaluable MRI assessment or no baseline data and no death within two cycles from baseline	Day 1	Censored

MRI, magnetic resonance imaging; PD, progressive disease; PFS, progression-free survival.

Based on the scheduled visit assessment scheme (i.e., every 4 cycles until Cycle 24 and every 6 cycles from then onwards), the definition of 2 missed visits will change over time and is calculated as the protocolled time between 2 subsequent scans + the protocol-allowed visit window for an early visit at the previous assessment + the protocol-allowed visit window for a late visit at the expected assessment:

Table 13: Two Missed Visits Window Rule

Scheduled assessments	Previous REiNS assessment	Two missed visits window
Q16w ± 1 week up to Week 80	Up to Week 15 (<Day 105)	33 weeks (231 days)
	Week 15 – Week 79 ≥105 - <553	34 weeks (238 days)
	Week 79 – Week 95 ≥ 553 - <665	42 weeks (294 days)
Q24w ± 1 week	Week 95 ≥665	50 weeks (350 days)

REiNS, Response Evaluation in Neurofibromatosis and Schwannomatosis.

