4.2.5.4 Primary Analysis of PFS

A KM plot of PFS will be presented including a patients-at-risk table. The percentage of PFS at Months 4, 8, 12, 16, 20, and 24 and every 6 months thereafter will be summarised based on the KM method. If more than 50% of patients progress in either arm, the median PFS and 95% CIs will also be calculated using the KM method and presented in the summary table.

Data are summarised and analysed using the Selumetinib FAS. Data are included as outlined in Sections 4.2.5.1 and 4.2.5.2, adhering to the intercurrent event strategy (refer to Section 4.2.5.3).

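### For placebo patients who cross over, the Extended Selumetinib FAS analyses of PFS, TTP and TTR reset the baseline scan but not the clock, adding a nominal 336 days in which no event can count

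*SAP*

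**What the plan says.** **Time origin.** SAP 4.2.5.1 says "PFS will be defined as the time from the date of randomisation until the date of progression by ICR per REiNS criteria", and 4.2.5.2 gives the only calculation rule: "The derivation formula for PFS is date of PFS event or censoring – date of randomisation + 1". Sections 4.2.6.1–4.2.6.2 (TTP) and 4.2.7.1–4.2.7.2 (TTR) use the same start. The SAP amendment history records the move from first dose to randomisation as a general change with no exception. Section 2, which lists departures from the protocol's planned analyses, does not mention it.

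**Protocol.** Section 9.4.2.3.3 computes PFS as "date of event or censoring – date of the first dose of selumetinib + 1", in the same section that resets the baseline scan for placebo patients. Sections 9.4.2.3.4 and 9.4.2.3.5 do likewise for TTP and TTR.

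**Extended Selumetinib FAS.** Membership requires at least one selumetinib dose (SAP 3.2.5). Baseline is the last value before selumetinib (3.3.1), and scans before the first selumetinib dose do not count as on-treatment (3.3.2.1). The supplementary bullets in 4.2.5.5, 4.2.6.5 and 4.2.7.5 repeat the baseline-scan reset and are silent on the clock. They also call for patient-level listings in months at DCO2 and DCO3.

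**Outputs.** In the Section 4.2 table the endpoint labelled "Progression-free survival (PFS) [single arm"] has analysis sets "Selumetinib FAS, Extended Selumetinib FAS, and FAS (selumetinib arm only") and summary measure "Percentage PFS at specified timepoints". Section 4.2.5.4 gives the timepoints: "The percentage of PFS at Months 4, 8, 12, 16, 20, and 24 and every 6 months thereafter will be summarised".

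**The concern.** Baseline scan and time origin belong together. The protocol moves both to the start of selumetinib for crossover patients. The SAP moves the scan and leaves the clock at randomisation. These patients then carry their whole placebo period as time at risk, although no event in it can count: placebo scans are excluded, and a patient who died on placebo never enters the set.

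Early crossovers show it most plainly. They switch because central review documented progression on placebo. That scan is discarded while the clock keeps running, so the patient is shown as progression-free since randomisation through a documented progression.

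At stake are the PFS, TTP and TTR results for the only set that uses every selumetinib-treated patient: the milestone percentages, any Kaplan-Meier curves, and the DCO2 and DCO3 listings. No alpha-controlled test is involved.

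**Working it through.** **Inputs**
- Cycle length 28 days; Cycle 12 Day 28 = Day 336 and Cycle 16 Day 28 = Day 448, each ±7 days (protocol 1.3, Schedule of Activities).
- Crossover after the end of Cycle 12 (protocol 6.3).
- Randomisation to first dose: at most 3 business days (Schedule of Activities, footnote e), taken here as up to 5 calendar days.
- Scans every 4 cycles from first dose up to Cycle 24 (SAP 4.2.1.1).
- One month = 365.25/12 = 30.4375 days.

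**1. Reproduce the schedule.** 12 × 28 = 336, which matches the Schedule of Activities. The first selumetinib dose for an on-schedule crossover is nominally Day 337.

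**2. Time in which no event can count.** 336 / 30.4375 = 11.0 months. With in-window visits the range is 336 − 7 = 329 days (10.8 months) to 336 + 7 + 5 = 348 days (11.4 months). A late visit would extend it.

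**3. Both formulas at the first scheduled scan on selumetinib (Day 448, randomised on Day 1)**
- SAP: 448 − 1 + 1 = 448 days = 14.7 months.
- Protocol: 448 − 337 + 1 = 112 days = 3.7 months.

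A response at that scan is therefore reported with a TTR of 14.7 months instead of 3.7.

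**4. Planned milestones, on-schedule crossovers.** Counted from randomisation, the first in-window scan on selumetinib falls between 441 and 455 + 5 = 460 days (14.5 to 15.1 months). Even the earliest is after Month 12 (365.25 days).

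| Milestone on the SAP clock | Days | Minus 336 | Months on selumetinib | What can be observed |
|---|---|---|---|---|
| 4, 8 | 121.75, 243.5 | none | 0 | PFS and TTP 100% by construction |
| 12 | 365.25 | 29.25 | 1.0 | 100% unless a death or unscheduled scan |
| 16 | 487.0 | 151.0 | 5.0 | about Month 5 on drug |
| 20 | 608.75 | 272.75 | 9.0 | about Month 9 on drug |
| 24 | 730.5 | 394.5 | 13.0 | about Month 13 on drug |

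**5. Early crossover.** A switch after the Cycle 4 or Cycle 8 scan adds at least 112 days (3.7 months) or 224 days (7.4 months). These are minimums, because the request and central review come between the scan and the switch.

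**6. Illustration, pooled display.** Assumed, not in the documents: 73 + 73 patients, all placebo patients crossing on schedule, exponential progression on selumetinib with 12-month risk q, scans every 112 days, follow-up to Day 672. By Month 12 the last scan on the selumetinib clock is at day 336, so PFS is S = (1 − q)^(336/365.25). On the SAP clock the crossover half has no events yet, so the pooled value is (1 + S)/2.

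| q | Selumetinib clock | SAP clock |
|---|---|---|
| 5% | 95.4% | 97.7% |
| 10% | 90.8% | 95.4% |
| 20% | 81.4% | 90.7% |

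**7. Day 1 for censoring.** SAP 3.3.3 ties Day 1 to the first dose of any study intervention, which for a crossover is placebo. If only the origin were moved, a crossover with no evaluable scan, censored at Day 1, would get 1 − 337 + 1 = −335 days. Day 1 has to move with the origin.

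**8. Missed-visit rule.** The reset baseline scan at Day 336 falls in the Table 13 row from Day 105 to before Day 553, with a window of 224 + 7 + 7 = 238 days. Table 13 therefore works unchanged on the Cycle 1 Day 1 calendar.

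**The case against.** The best defence is that this is a gap rather than an intended rule. The intercurrent-event sections for these endpoints say the analysis is on patients randomised to selumetinib, so the definitions look written for the Selumetinib FAS. Everything else about the extended set is anchored to selumetinib: baseline, eligible scans, and the DOR bullet, which refers to first response to selumetinib. A careful programmer might infer the right origin. This does not remove the problem. The amendment entry is general, no exception is written, and a program that follows the stated formula gives the wrong times.

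It can also be said that the milestones in 4.2.5.4, 4.2.6.4 and 4.2.7.4 are stated for the Selumetinib FAS, so their use for the extended set rests on the Section 4.2 table. That is fair, but the table names the set explicitly, and the listings are specified separately.

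The display point is weaker. The condition "If more than 50% of patients progress in either arm" may be carried-over wording, since it sits in a section analysed on one arm. The SAP simply does not say whether extended-set results are pooled or shown by randomised arm. By arm, only the crossover curve is wrong; pooled, one curve mixes two time scales.

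The limited reach stands in full: the outputs are supplementary and descriptive, and no decision rule uses them. The omission from Section 2 is editorial, because the change is disclosed in the amendment history.

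**Conclusion.** The point holds as written and should be fixed. For on-schedule crossovers the SAP clock adds a nominal 336 days (11.0 months) to PFS, TTP and TTR in the Extended Selumetinib FAS. PFS and TTP are 100% at Months 4, 8 and 12 barring a death or an unscheduled scan, and later milestones represent about 11 months less treatment than their label. If the approximately 10-month median TTR cited in protocol 4.2 applied to crossovers, it would be reported as 10 + 11.0 = 21.0 months; that is illustration only.

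The 336 days rests on the protocol schedule and on crossover at the planned time. The pooled percentages rest on assumed progression risks. The main Selumetinib FAS analyses move by at most 3 business days, and randomisation is a defensible origin there because the SAP's set includes patients never dosed. DOR is unaffected because its clock starts at first response.

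**What to change.** 1. In SAP 4.2.5.5, 4.2.6.5 and 4.2.7.5, state that for the Extended Selumetinib FAS the time origin, and Day 1 for censoring, is the date of first selumetinib dose.
2. State whether extended-set results are pooled or shown by randomised arm, and make the single-arm label in the Section 4.2 table consistent with the either-arm condition in 4.2.5.4 and 4.2.6.4.
3. List the change of origin in SAP Section 2.
4. Leave Table 13 on the Cycle 1 Day 1 scan calendar, with the reset baseline scan as the previous assessment. Randomisation can stay as the origin for the Selumetinib FAS.

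Cost: one sentence in each of three supplementary sections, a short display statement, one entry in Section 2, and a population-specific start date in the time-to-event derivations. No new data are needed.
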